8.1.8 Medical Dictionary Coding

Medical dictionary coding will be performed using a coding thesaurus algorithm. The MedDRA will be

used upon data entry and query resolution for AEs, SAEs, via automated and manual coding processes.

8.1.9 Data Quality Assurance

Quality control and quality assurance processes implemented during this study to ensure subject safety rights, and welfare are protected and to foster data integrity are characterized below.

8.1.10 Investigator Training - Protocol Specific Training

Protocol training will be scheduled once IRB approval is obtained and the Clinical Study Agreement is executed. AtriCure, Inc. will train the study site on the protocol and that training will be documented. It is ultimately the responsibility of the Investigator to ensure all clinical site personnel participating in this study are trained.

The index procedure may only be performed by qualified investigators, familiar with the study procedures and techniques.

Investigators will also be required to complete training in the use of the AtriCure® *cryoICE* cryo-ablation system through didactic and hands on training, including review of an instructional video on the use of the AtriCure® *cryoICE* cryo-ablation system.

8.1.11 Monitoring

This study will be monitored by the sponsor to ensure:

- The rights, safety and well-being of the subjects are protected;
- The reported study data is accurate, complete, and verifiable from source documents; and
- The conduct of the study is in compliance with the currently approved protocol/amendment(s), applicable GCPs, and with applicable local/regional regulatory requirements.

AtriCure, as Sponsor of this study, will be responsible for monitoring this study. The Clinical Research Associate (CRA) duties are to aid the Principal Investigator in the production and maintenance of complete, legible, well-organized and easily retrievable data. In addition, the CRA will be responsible for assuring the Principal Investigator understands the protocol and all applicable regulations. Approaches to monitoring include on-site visits and may include a remote visit, as appropriate and the rationale and frequency for monitoring will be at the Sponsor's discretion. The extent and nature of monitoring will be predetermined and based on considerations such as the objective, design, complexity, and endpoints of the study and mutually agreed to by the Sponsor. The frequency of monitoring will be determined for each site based on factors including: the planned enrollment, the rate of enrollment, and the current study conduct. Study conduct can be evaluated remotely based on compliance percentage, discrepancy rate and discrepancy type. CRAs will be trained on and comply with established standard operating procedures as well as a written monitoring plan specified by the Sponsor.

In order to perform the monitoring role effectively, the CRA must verify eCRF entries with source documents. The CRA must be given access to primary subject data which supports the information recorded on the eCRF, i.e. hospital notes, appointment books, original laboratory records, etc. Access to these documents must also be given should the regulatory authority in the instance of an external inspection. Since a subject has the right to refuse access to these documents on the grounds of

confidentiality, consent to access is included in the informed consent document, which the subject signs.

The Principal Investigator will receive reasonable notification prior to each monitoring visit during the course of this clinical investigation. At each visit, the Principal Investigator will be expected to co-operate with the CRA for the review and verification of eCRFs and any additional records that may have been previously arranged between the Principal Investigator and the CRA.

8.2 Changes to Protocol, Protocol Deviations and Protocol Amendments

8.2.1 Changes to Protocol

The Investigator should not implement any deviation from, or changes to the protocol without agreement by the sponsor and prior review and documented approval/favorable opinion from the IRB of an amendment, except where necessary to eliminate an immediate hazard(s) to study subjects, or when the change(s) involves only logistical or administrative aspects of the study (e.g., change in CRA(s), change of telephone number(s)). In the event of an emergency situation, the Investigator must notify the CRA or AtriCure immediately. A full written report of the situation must be forwarded to the IRB who approved the original protocol and AtriCure within 10 working days of the event.

8.2.2 Protocol Deviations

The Investigator agrees to conduct the study in accordance with this protocol; however, protocol deviations may occur during the course of the study. Protocol deviations are events occurring during the conduct of the study which are not in compliance with the protocol and for which an amendment has not been granted. Protocol deviations can be committed by the Sponsor, the PI, or study subject. A deviation can be identified from a number of sources. Potential sources include, but are not limited to: a member of the PI's staff, the CRA during monitoring visits, or a member of the data management or statistical groups when entering or analyzing data. The PI or PI's representative are encouraged to contact the CRA or AtriCure as soon as possible upon observing a protocol deviation. Regardless of the source, it is crucial to document the deviation and record all corrective actions. Protocol deviations will be reported in the final report.

The process for capturing deviations will be detailed in the monitoring plan. The process will require that documentation describe the deviation, appropriate actions taken, and will be included in the study file for the respective PI and subject. The study site representative will be advised to record the deviation and relevant discussion with the Sponsor about the deviation in subject source documents.

Protocol deviations affecting the scientific soundness of the study or the rights, safety, or welfare of the subjects, will be reported by the PI, as required by the IRB.

Protocol deviations will be summarized and grouped into relevant categories for analysis and may include, but not be limited to, subjects who:

- Entered the study although they did not satisfy the eligibility criteria; or
- Developed withdrawal criteria during the study, but not removed.

8.2.3 Protocol Amendments

If it becomes necessary to amend the protocol then the nature of the amendment will be agreed between the Sponsor and the Principal Investigator(s) and this will be recorded with a justification for the

amendment. The appropriate IRBs will be informed of amendments prior to implementation of the change.

9.0 STATISTICAL METHODS

9.1 Clinical Study Objective

The objectives of this study are to:

1. To demonstrate that intraoperative intercostal cryoanalgesia provides improved analgesic efficacy in patients undergoing unilateral thoracotomy cardiac procedures as compared to current intraoperative standard of care.
2. Long-term goal is to elucidate complementary strategies for enhanced postoperative pain management of patients at risk for postoperative pulmonary complications from unilateral thoracotomy cardiac procedures.

Completion of the proposed study will for the first time demonstrate efficacy of intercostal cryoanalgesia in patients undergoing minimally invasive heart valve surgery. Furthermore, results of this study may have a pivotal role in supporting future clinical outcome trials for intercostal cryoanalgesia therapy.

9.2 Study Endpoints

The following endpoints will be collected for this study:

Co-Primary Endpoints:

1. Forced Expiratory Volume (FEV₁) at 48-hours post-surgery
2. Visual Analogue Scale (VAS) pain in the surgical region at 48-hours post-operative

Secondary Endpoints:

1. Spirometry assessments including: forced expiratory volume (FEV₁), forced vital capacity (FVC) and slow vital capacity (SVC) at 48-hours post-extubation and other designated time points during hospital admission
2. Pain in the surgical region assessed via Visual Analogue Scale (VAS) pain at 72-, 96- and 120-hours (as long as patient remains in hospital up to 120-hours) post-operative
3. Allodynia at 3 and 6 months
4. Duration of oral endotracheal intubation defined as hours until patient is extubated from time patient leaves the operating room
5. Patient Controlled Analgesia (PCA) and oral opioid consumption up to each time point (24-, 48, - 96 and 120-hours) and total PCA and oral opioid consumption after extubation
6. ICU length of stay and hospital length of stay
7. Ambulatory movement

9.3 Sample Size and Power

In a couple of previous studies^{10,11} of cyro-analgesia on patients undergoing thoracotomy the authors FEV1 was collected at 48-hours post-procedure and at other specified time-points. The studies reported 48-hours FEV1 mean (SD) values of 1.5 (0.7) and 1.1 (0.47) in their standard of care (continuous analgesia and

Study Number: CP2015-4

CONFIDENTIAL

Page 29 of 39

Record: Clinical Study Protocol

Version date: 31May2016 / Rev: D

epidural fentanyl infusions) groups. We used a mean mid-point of 1.3 and a liberal standard deviation of 0.39 as reasonable estimates for sample size calculation. The investigators participating in this trial agree that based on their prior experience a 20% improved FEV1 value (compared to SOC) is a reasonable expectation. Based on this assumption, the expected mean (SD) for the Study Group is 1.56 (0.39), assuming a common standard deviation.

This is a prospective, multicenter, randomized (3:1). Group sample sizes of 75 (Study Group) and 25 (Control Group) will achieve 80% power to reject the null hypothesis of equal means when the population mean difference is 0.26 with a standard deviation for both groups of 0.39 and with a significance level (alpha) of 0.05 using a two-sided two-sample equal-variance t-test.

Also, in a previous preliminary observational study of six patients undergoing single cardiac valve surgical procedure via right anterior mini-thoracotomy comparing a Visual Analogue Scale (VAS of 0-10) pain was collected at 0, 24, and 48 hours post-procedure. Mean VAS pain differences of 1.5 and 1.8 between the intercostal Cryoanalgesia group and the SOC group at 24 and 48 hours were statistically significant with p-values of 0.03 and 0.04, respectively. The common standard deviation at 48 hours post-procedure was 2.2.

Group sample sizes of 75 (Study Group) and 25 (Control Group) will achieve 94% power to reject the null hypothesis of equal means when the population mean difference is 1.8 with a standard deviation for both groups of 2.2 and with a significance level (alpha) of 0.050 using a two-sided two-sample equal-variance t-test.

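### Does the pilot p-value of 0.04, which a t-test on six patients does not reproduce, undermine the VAS power calculation?

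*Combined protocol and SAP*

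**What the plan says.** The second half of section 9.3 (Sample Size and Power) takes its VAS assumptions from pain scores collected at 0, 24 and 48 hours "in a previous preliminary observational study of six patients undergoing single cardiac valve surgical procedure via right anterior mini-thoracotomy". It states: "Mean VAS pain differences of 1.5 and 1.8 between the intercostal Cryoanalgesia group and the SOC group at 24 and 48 hours were statistically significant". The p-values given are 0.03 at 24 hours and 0.04 at 48 hours. It adds: "The common standard deviation at 48 hours post-procedure was 2.2". It gives no SD at 24 hours, no split of the six patients between groups, no name for the test, no sidedness, and no mention of any adjustment.

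The power statement follows: "Group sample sizes of 75 (Study Group) and 25 (Control Group) will achieve 94% power" to reject equal means "when the population mean difference is 1.8 with a standard deviation for both groups of 2.2", at a two-sided alpha of 0.05 with an equal-variance t-test. No other source is cited for 1.8 or 2.2.

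**The concern.** A reader who puts the printed pilot figures into a t-test finds that they disagree. With six patients, a difference of 1.8 and an SD of 2.2, the difference is about one standard error. That is far from significant, yet the text reports p = 0.04. Either one of the four figures (sample size, difference, SD, p-value) is misreported, or the p-value comes from an analysis that the text does not describe.

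This looks serious because 1.8 and 2.2 are the only effect inputs to the power for a co-primary endpoint, and the claim of significance presents 1.8 as an observed effect rather than a working assumption. If the difference or SD were the misreported figure, the 94% could be too high or too low.

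**Working it through.** **Inputs, all from section 9.3.** Pilot: 6 patients in total, 48-hour difference 1.8, common SD 2.2, p = 0.04. Trial: 75 vs 25, difference 1.8, SD 2.2, two-sided alpha 0.05, equal-variance t-test.

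**1. The plan's own figure.** The standard error is 2.2 × √(1/75 + 1/25) = 0.508, and the noncentrality is 1.8 / 0.508 = 3.54 on 98 df. Power from the noncentral t is 93.9% (94.3% by the normal approximation). The stated 94% is correct for its inputs, and the pilot p-value does not appear in the formula.

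**2. The pilot p-value.** t = 1.8 / (2.2 × √(1/n₁ + 1/n₂)), df = n₁ + n₂ − 2.

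| Split | SE | t | df | Two-sided p |
|---|---|---|---|---|
| 3 vs 3 | 1.796 | 1.002 | 4 | 0.373 |
| 2 vs 4 | 1.905 | 0.945 | 4 | 0.398 |
| 1 vs 5 | 2.410 | 0.747 | 4 | 0.497 |
| 6 vs 6 (if six means per group) | 1.270 | 1.417 | 10 | 0.187 |

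The most favourable rounding (1.85 and 2.15, 3 vs 3) gives 0.351. The best one-sided value for six patients is 0.187. At 3 vs 3 the 95% interval for the difference is 1.8 ± 2.776 × 1.796, or −3.2 to 6.8.

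**3. What would give 0.04.** At 3 vs 3 with a difference of 1.8, the SD would have to be 1.8 / (2.999 × √(2/3)) = 0.74. With SD 2.2, about 14 per group are needed (p = 0.0398). Adjusting for the 0-hour score, with the groups equal at 0 hours, leaves 3 df and a critical value of 3.48. The residual SD must then be 1.8 / (3.48 × √(2/3)) = 0.63. Setting 2.2 × √(1 − r²) = 0.63 gives r of about 0.96.

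**4. Whether any unadjusted test could give 0.04.** An exact two-sided rank-sum test on six patients cannot go below 2/20 = 0.10. The large-sample, tie-corrected form without continuity correction can. Scores of 0, 5.25, 5.3 against 5.35, 5.35, 5.35 have a difference of 1.83, a pooled SD of 2.15 and p = 0.037, which print as 1.8, 2.2 and 0.04. The example is contrived, and no such 3/3 set was found on whole-point or half-point scores. It shows only that the printed figures are not strictly impossible.

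**5. 24 hours.** No SD is given, so no inconsistency can be shown. A difference of 1.5 with p = 0.03 at 3 vs 3 corresponds to an SD of 0.56.

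**6. What hangs on it.** Trial power at 75 vs 25, by which figure is taken to be wrong:

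| Assumption | Power |
|---|---|
| Only the pilot sample size or p-value is wrong | 93.9% |
| SD is really 0.74 | over 99% |
| SD 2.2, difference 1.5 (illustrative) | 83% |
| SD 2.2, difference 1.0 (illustrative) | 50% |

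Power is 80% at a difference of 1.44 with SD 2.2, or at an SD of 2.75 with a difference of 1.8.

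**The case for a change.** The best case for asking for a change is that the contradiction sits in a single paragraph, is roughly tenfold on the p-value scale, and concerns the only source given for the effect inputs of a co-primary endpoint. The innocent explanations are strained: baseline adjustment needs a very high correlation, and the rank-sum example is artificial. A paired analysis of six patients with strong within-patient correlation could give a small p, but the text describes a comparison between two groups. The remedy would also be cheap: check the pilot data and reword one paragraph.

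Much of this stands. The p-value does not match a t-test on the printed figures, and six patients are weak support for any assumption: an SD of 2.2 on 4 df has a 95% interval of about 1.3 to 6.3. But that weakness is plain from the stated pilot size, whatever the p-value. The objection does not show that 1.8 or 2.2 is wrong, and a planning assumption need not be statistically significant in a pilot to be used. Cheapness is not a reason either if the correction leaves the trial as it was.

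**Conclusion.** The mismatch is confirmed under the t-test (p of at least 0.37 against a reported 0.04), but it is a reporting flaw in background material and no change to the plan follows. The pilot p-value feeds nothing. The 94% is correct for its stated inputs and would read the same if the significance claim were struck out. The document does not show which pilot figure is off, or whether an unreported analysis explains it, so it gives no better value of 1.8 or 2.2 to use.

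There is also some margin. VAS power holds at 80% or more for differences down to 1.44 (SD 2.2) or SDs up to 2.75 (difference 1.8), each varied alone. FEV₁ is the tighter of the two co-primary calculations, at a stated 80% with the same 75 and 25 patients. The VAS test in section 9.6.1 will use the trial's own means and variances, so the pilot cannot affect the result.

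This rests on the power statement being read as it is written, conditional on an assumed difference and SD. If the pilot source showed that 1.8 or 2.2 was itself misreported, the quoted power would need recalculating; the document gives no evidence of that.

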9.4 Randomization

Upon enrollment, subjects will be assigned a sequential identification number at each site and a corresponding sealed envelope which will be opened prior to the procedure to reveal the treatment group. Subjects will be randomized 3:1 (3 intercostal Cryoanalgesia in conjunction with SOC and 1 SOC). Randomization sequences will be generated by AtriCure Statistician using SAS version 9.4 (SAS Institute Inc., Cary, North Carolina) and will be stratified by site.

9.5 Analysis Populations

Intent-To-Treat (ITT) Population: The effectiveness, safety and health economics analyses will be based on the ITT population. The ITT Population is defined as all subjects randomized to either the Study Group or SOC Group and on whom the surgical index procedure is attempted (even if the index procedure is aborted).

Per-Protocol (PP) Population: A PP population may be defined for effectiveness and health economics and analyses. This population is defined by ITT population but without any major protocol violations, that is, those that could potentially bias the results.

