4.2.5 Removal of Subjects from Study

In accordance with the Declaration of Helsinki and the Code of Federal Regulations, a subject has the right to withdraw from the study at any time for any reason without prejudice to his/her future medical care by the physician or the institution. Should a subject (or subject's legally authorized guardian/representative) decide to withdraw; all efforts will be made to collect and report the final visit observations as thoroughly and timely as possible. Subjects who withdraw from the study will not be replaced.

The primary reason for early termination and the date of termination will be recorded in the electronic case report form. Reasons may include:

Investigator Decision

If the subject experiences an adverse event and the Principal Investigator or Medical Monitor believes it is in their best interest to discontinue participation in the study, they will be withdrawn from the study.

Lost to Follow-up

When contact with the subject has been lost without completing the final visit assessment, and every attempt to contact has failed, the subject will be considered lost to follow-up. Attempted contact with the subject should include 2 attempted phone calls and the sending of a certified letter before the subject can be considered lost to follow-up. Final documentation regarding all attempts to contact the subject requesting their return for the final visit should be documented.

Withdrawal of Consent

The subject withdraws consent for participation in the study. Any method of contact with the subject in which they state they no longer want to participate in the study specific activities constitutes withdrawal of consent. When possible the reason for withdrawal will be documented.

Site Termination or Study Termination

A site or study may be terminated. When this occurs all subjects at the site will be withdrawn and documented as early termination. Reasons for site or study termination may include, but are not limited to the following:

- Administrative Concerns (e.g., inadequate subject enrollment, Investigator/institution non-compliance, change of business strategy, etc.);
- Safety Issues, including those due to non-compliance, which substantially affect the risk to benefit ratio of the study subjects at a site or for the study as a whole;
- Regulatory Body Mandate(s)

Other (which may include):

- Protocol deviation, noncompliance or violation
- Sponsor recommendation
- Device/index procedure failure
- Death

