5.0 PROCEDURE

5.1 General Description

Individual centers and investigators will be selected based upon their expertise in unilateral thoracotomy cardiac procedures as well as proficiency in cryoanalgesia using the AtriCure® *cryoICE* cryo-ablation system.

The protocol term “index procedure” refers only to the use of the *cryoICE* system. All procedures leading up to and after the use of the *cryoICE* system are considered part of the unilateral cardiac thoracotomy procedure and are to be conducted under the discretion of the surgeon in accordance to the hospital’s standard of care.

If the subject meets all study eligibility criteria, they will be enrolled and randomized. If the subject is randomized to the group to receive the Intercostal Analgesia by using the AtriCure® *cryoICE* cryo-ablation system, the following steps are performed:

*Note: A recommended surgical technique is presented below. It is recognized that individual patient anatomic variation, surgical conditions, or surgeon preference may necessitate modifications to the outlined procedures. Regardless, surgeons must adhere to the instructions for use for the AtriCure *cryoICE* Probe (CRY02) as outlined in the IFU.*

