7.2 Visit 2 – Index Procedure

- Targeted Physical Exam (prior to Index Procedure)
- Vital Signs (prior to Index Procedure)
- VAS (prior to Index Procedure)
- Index Procedure (Study Arm - Intercostal Analgesia or Control Arm – SOC Pain Management)
- Concomitant Procedure Type
- Concomitant Medication Review
- Adverse Events Assessment
- Date and Time Subject Exits Surgical Suite

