9.6.2 Safety Analysis

AEs related to the CryoAnalgesia procedure or device will be reported on the eCRF. These AEs will be listed and descriptively summarized for patients in the Study Group. No formal statistical hypothesis will be tested.

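### Related adverse events are summarised for the assigned Study Group only, so a control who receives cryoanalgesia is exposed to the device but falls outside the planned summary

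*Combined protocol and SAP*

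**What the plan says.** Section 9.5 (Analysis Populations) sets the safety analysis set: "The effectiveness, safety and health economics analyses will be based on the ITT population". That population consists of "all subjects randomized to either the Study Group or SOC Group", restricted to those "on whom the surgical index procedure is attempted (even if the index procedure is aborted"). The optional per-protocol set is described for effectiveness and health economics only. No safety or as-treated set is defined, and no rule covers patients who receive the other arm's treatment.

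Section 9.6.2 (Safety Analysis) covers events related to the cryoanalgesia procedure or device: "These AEs will be listed and descriptively summarized for patients in the Study Group". It adds: "No formal statistical hypothesis will be tested". Section 10.2.4 requires related events on the eCRF with no restriction by arm.

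The term index procedure has more than one meaning. Section 5.1 says that it "refers only to the use of the" cryoICE system. The visit list in section 7.2 has "Index Procedure (Study Arm - Intercostal Analgesia or Control Arm – SOC Pain Management"), so there it also covers control care. Section 9.5 uses a third phrase, surgical index procedure, and applies it to both arms.

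**The concern.** A device-safety summary should describe the patients exposed to the device. Here the set is built from assignment, and the display is then cut to one assigned group. A control who receives cryoanalgesia can have a device-related event that reaches the eCRF but has no row in the summary.

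Such a crossover is possible. Under section 6.1 the probe is a commercial product that the sponsor does not supply, and under section 5.1 sites are chosen for proficiency with it. Section 4.2.5 also foresees "Device/index procedure failure" as a reason for early termination, so incomplete treatment is anticipated. That entry does not show that such a patient had no exposure.

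At stake are the completeness of the adverse-event summary and a clear denominator for it. Section 12.1 anticipates no independent oversight, and Appendix 3 puts several device risks above 10%, so readers will rely on this summary.

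**Working it through.** **1. Planned denominator.** The plan states no safety figure. Section 9.3 gives 75 Study Group and 25 Control subjects. Its powers reproduce with a two-sided equal-variance t-test at 0.05 (noncentral t): 81.6% for FEV1 (difference 0.26, SD 0.39; stated 80%) and 93.9% for VAS (difference 1.8, SD 2.2; stated 94%). I therefore use 75 and 25.

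**2. Who is counted under each meaning of index procedure.**

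| Meaning | Control given cryo | Study Group patient, device use never attempted |
|---|---|---|
| Use of cryoICE only (5.1) | In ITT, not in the 9.6.2 summary | Not in ITT |
| Arm-specific (7.2) | In ITT as a control, not in the 9.6.2 summary | Not in ITT |
| The operation (a possible reading of 9.5) | In ITT, not in the 9.6.2 summary | In ITT and in the denominator |

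The gap for the treated control appears under all three meanings, provided that Study Group means as randomised. The denominator problem appears only under the third. That meaning cannot be dismissed: under the first, an untreated control could never enter the ITT set, although section 9.5 includes the SOC Group.

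**3. Size of the treated-control gap.** The documents give no crossover rate, so the number of treated controls, c, is an assumption. If all 75 Study Group patients are treated, the share of exposed patients omitted is c/(75 + c). With event risk p and independent patients, the chance that at least one affected patient is omitted is 1 − (1 − p)^c.

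| c | Share omitted | p = 5% | p = 10% | p = 20% |
|---|---|---|---|---|
| 1 | 1/76 = 1.3% | 5% | 10% | 20% |
| 2 | 2/77 = 2.6% | 10% | 19% | 36% |
| 3 | 3/78 = 3.8% | 14% | 27% | 49% |

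The rate can move either way. Take 8 events in the Study Group, 8/75 = 10.7%. Adding one treated control gives 9/76 = 11.8% if that patient has an event and 8/76 = 10.5% if not.

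**4. Size of the denominator effect.** Let k of the 75 have no device contact; k is also an assumption. If related events arise only in exposed patients, the reported rate is p(75 − k)/75, a relative reduction of k/75.

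- k = 1: 1.3% relative; a true 10% is reported as 9.9%.
- k = 4: 5.3% relative; 10% is reported as 9.5%.
- k = 8: 10.7% relative; 10% is reported as 8.9%.

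With 8 events and k = 4, the comparison is 8/75 = 10.7% (exact 95% CI 4.7% to 19.9%) against 8/71 = 11.3% (5.0% to 21.0%). The shift is small beside the interval.

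**5. Aborted cases with device contact.** These patients are exposed and belong in the denominator. Suppose 4 aborted cases had 2 related events and the other 71 patients had 7. Keeping them gives 9/75 = 12.0%; removing them gives 7/71 = 9.9%. Removing them would lower the rate.

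**The case against.** The strongest reply is that little is lost. Section 9.6.2 is descriptive, related events are collected whatever the arm, and section 8.2.2 puts protocol deviations in the final report. Sections 10.0 and 11.1 add device and complaint reporting, and section 9.6.1 compares allodynia between both groups. Section 9.6 allows further analysis populations, and section 9.7 allows a detailed plan. The documents also never say outright that adverse events are grouped as randomised.

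Most of this stands as a limit on size. The treated control's event is missing from a summary, not from the record, and that summary is not the trial's only safety information. But sections 9.6 and 9.7 only permit another set, while section 9.5 states the rule in force, and its definition ties group to randomisation.

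A reader might also infer that counting aborted procedures dilutes the event rate, so that device risk is understated. The documents do not support that. Section 9.5 requires an attempt, and section 5.1 equates the index procedure with use of the device. On that reading an aborted case is one in which device use was attempted, and it may carry an event. Dilution needs a patient with no device contact, and so the broader meaning of the term.

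**Conclusion.** The point holds in limited form. If Study Group means as randomised, as section 9.5 indicates, a control who receives cryoanalgesia falls outside the planned adverse-event summary under every meaning of index procedure. A Study Group patient with no device contact may also be counted, depending on a term that the protocol uses inconsistently.

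The effect is probably small. On the assumptions shown, 1.3% to 3.8% of exposed patients are omitted for 1 to 3 treated controls. With 1 to 8 unexposed Study Group patients, a 10% rate would be reported as 9.9% to 8.9%. Neither range rests on a rate in the documents, and the overall direction of any error is not fixed. The case for change is that the rule as written does not follow exposure, and that correcting it is cheap.

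**What to change.** - In section 9.5, remove safety from the ITT sentence. Define a Safety Population of all patients in whom the cryo device was applied or its use attempted, whatever the assigned arm, analysed by treatment received.
- Keep aborted cases in this set and flag them. Do not require a freeze for entry: Appendix 3 lists device breakage and tissue perforation, which could occur without one.
- Report section 9.6.2 on this set. List untreated Study Group patients and treated controls separately.
- Reconcile the meaning of index procedure across sections 5.1, 7.2 and 9.5.

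A comparison group of patients without device exposure is not worth adding. Sections 7.11 and 10.2.4 put only cryo-related events on the eCRF, so that group would have almost none by construction.

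The cost is a change of wording, provided that treatment received and aborted attempts are recorded for every patient. The stated event rate may change slightly, in either direction.
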